11.2.1.1 Radiographic criteria

Adams stage 2-4 classification (Adams et al., 1986), with (fibrous ring capable of contain the cell implant), used for inclusion or exclusion purposes in the assay. In profile radiography carried out with the same technical characteristics and times (before noon) the height of the intervertebral space in millimeters will be measured, this being the

variable that will be compared with the measurements that occurred over time (6 and 12 months after MSV implantation). An increase in height will be understood as an indication of rehydration disc associated with an increase in proteoglycans and cellularity of the NP. Descriptive analysis of the observed values will be expressed by the mean, standard derivation, interval of 95% confidence of the mean. To find out if there are differences between baseline and at 6 and 12 months the Wilcoxon nonparametric test for paired data will be used. So Optional, the study will be repeated at 12 months evaluating changes in the leading. The analysis descriptive of the observed values will be expressed by the mean, standard deviation, 95% confidence interval of the mean.

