5.1 INCLUSION AND EXCLUSION CRITERIA

5.1.1. Inclusion criteria

1. Lumbar degenerative disc disease of one or two discs with predominance of pain lumbar and / or persistent sciatica after conservative treatment (medical and physiotherapy) of more than 6 months of evolution.

2. Complete fibrous ring, capable of containing the cellular implant, demonstrated with in the MR image (Adams stages 2, 3 and 4) (Adams et al., 2000).

3. Decrease in the height of the disc space of more than 20% measured

radiographically in lateral image.

4. Absence of spinal infection.

5. Hematological and biochemical analyzes without significant alterations that contraindicate intervention

6. The patient is able to understand the nature of the study.

7. Written informed consent of the patient.

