5.2.2 Imaging Criterion

5.2.2.1 Radiography.

The intervertebral space decrease of more than 20% in the profile projection in comparison with healthy adjacent segments is a criterion used for the purpose of inclusion or exclusion in the trial.

The classification of degeneration by discographic criteria will be carried out according to the staging Adams (Adams et al., 1986):

1. Cotton ball. No signs of degeneration

2. Lobular. Nucleus pulposus amorphous, soft and white

3. Irregular. Mature disc, with nucleus pulposus beginning to merge and with fibrous fragments

4. Cracked. Degenerated disc, with fissures and cracks in the nucleus pulposus and in the inner part of the annulus fibrosus

5. Broken. Degenerated disc, with radial fissure that reaches the outer edge of the annulus fibrosus

A lateral x-ray in standing and flexion-extension will be taken to assess the excess of mobility in the pathological segment and its evolution during treatment.

5.2.2.2 Magnetic Resonance Imaging (MRI):

T2 and STIR (short T1 inversion recovery) sequences will be performed in the axial and sagittal. They will be carried out at the beginning and 6 and 12 months after the intervention. It will be carried out quantification of the water content of the disc on the T2 image without contrast as described in detail in section 3.3 (see Figure 4). The MRI image will also be used to assess the integrity of the external fibrous ring at the inclusion visit.

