7.2.1. Visiting Program

Pre-Inclusion: In patients who come for consultation and whose medical history and examinations complementary, including X-rays and / or MRI, presume an orientation diagnosis with the possibility of inclusion in the trial, presenting all the criteria of inclusion and none of exclusion, the treatment regimen will be prescribed according to the standard and then they will be informed of the possibility of inclusion in the EC. They will deliver the "Patient Information Sheet" (Annex II) and, if its decision is affirmative, Inclusion procedures will begin on a future visit.

Visit 0. Inclusion. May comprise more than one physical visit. If the patient confirms that want to join the trial, you will be asked to sign the "Consent Document Informed "(Annex II). You will be ordered new MRI and radiographic scans with the mandatory characteristics of the study unless these examinations had already been performed previously within a period of no more than 6 months. Completed analytics will be requested with the regulated serology for determination of HIV, Hepatitis and Lúes and test of pregnancy if you are a woman of childbearing age. Although positive serology is not a reason for exclusion in this trial, it will be done for epidemiological reasons. After checking the inclusion and exclusion criteria, the clinical history will be made, including data referring to low back pain and discopathy, treatments carried out, analytics and imaging tests to define the characteristics of the same and carry out the measurements that will be taken as a standard of future explorations. Low back pain evaluation questionnaires will be passed (VAS), disability (Oswestry) and quality of life (SF-12). It will be scheduled on the day of the intervention (V1) and the X-ray and MRI tests will be performed, if they had not already been performed.

Visit 1 (day 1). Placebo injection or allogeneic MSV, depending on the clinical trial arm. Visit 2 (8 days): Safety assessment. Includes analytical control.

Visit 3 (3 months): Safety assessment. EVA, Oswestry and SF-12 questionnaires. RX. Visit 4 (6 months): Safety assessment. EVA, Oswestry and SF-12 questionnaires. RX. RM.

Visit 5 (12 months) Safety assessment. EVA, Oswestry and SF-12 questionnaires. RX. RM.

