11.2 STATISTICAL METHOD USED

In all descriptive analyzes, categorical variables will be summarized using frequencies and category percentages. For the distributions of continuous variables, will present the mean and its Standard Deviation, the median and the 25th and 75th percentiles of the distribution, the number of cases, minimum and maximum value.

All hypothesis tests will be two-tailed, with a significance level of 5%. The The result of a hypothesis test will comprise the 95% Confidence Interval of the variable (s) analyzed. To calculate the statistical significance of the differences between the two groups, a normality analysis of the distribution will be carried out and compare the means using the double-tailed t-test or the Wilcoxon, depending on whether the population is Gaussian or not.

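### Where the X-ray that qualifies a patient also serves as the disc-height baseline, regression to the mean biases within-arm height change upward, and section 11.2.1.1 would read that rise as rehydration

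*Combined protocol and SAP*

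**What the plan says.** **Entry.** Section 5.1.1, criterion 3, requires "Decrease in the height of the disc space of more than 20% measured" on a lateral radiograph. Section 5.2.2.1 gives the reference: "The intervertebral space decrease of more than 20% in the profile projection in comparison with healthy adjacent segments is a criterion used" for inclusion or exclusion.

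**Outcome.** Section 3.3.1 lists disc-space height in millimetres on the profile film as a primary criterion. Section 11.2.1.1 makes it the "variable that will be compared with the measurements that occurred over time (6 and 12 months after MSV implantation"). For baseline against 6 and 12 months, "the Wilcoxon nonparametric test for paired data will be used". On interpretation it says "An increase in height will be understood as an indication of rehydration disc". Section 11.2 sets two-tailed tests at 5%.

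**Which film is the baseline.** Three places bear on this, and they differ.
- The schedule table in 7.2 marks the lumbar X-ray at pre-inclusion, 6 months and 12 months. It has no mark at V0, whereas the MRI row does.
- Section 4.2 schedules radiographs after consent as the reference for later change, but allows recent valid films to be used instead. It also has the inclusion criteria verified again at V0.
- Section 7.2.1 (Visit 0) orders new films unless existing ones are no more than 6 months old. After the eligibility check, staff are to "carry out the measurements that will be taken as a standard of future explorations".

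**The concern.** Entry admits patients whose measured disc space is low. Part of any low reading is measurement error, and near a cut-off the error that lets a patient in goes in one direction. If the same reading is the baseline, an independent reading at 6 or 12 months will on average be higher even when the disc has not changed. This differs from ordinary noise around an unselected baseline, because the mean change itself is shifted.

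The stated height analysis has no defence against this. It tests each arm against its own baseline, treats any increase as a sign of rehydration, and does not refer to the control arm. A rise in the MSV arm could therefore be reported as regeneration, on a criterion that 3.3.1 calls primary, when the entry rule alone produced it.

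**Working it through.** **1. Inputs from the documents.** Threshold 20% narrowing (5.1.1, 5.2.2.1); paired Wilcoxon, two-sided 5%, so 2.5% nominal in the upward direction (11.2, 11.2.1.1); 12 patients per arm (11.1). The plan gives no power calculation, height SD or measurement error, so there is no figure of its own to reproduce.

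**2. Assumptions, not in the documents.** True narrowing T among screened candidates is Normal with mean μ = 20, 25, 30 or 35% and SD 10 points. Reading error is independent between films, with SD σe = 3, 5 or 8 points. There is no true change. One point is one hundredth of the healthy neighbour's height, or 0.1 mm if that height is 10 mm.

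**3. Expected spurious gain.** The qualifying reading is X = T + e, and the patient enters if X > 20. If X is also the baseline, the expected height gain at follow-up is

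E[e | X > 20] = (σe² / σX) × φ(a) / [1 − Φ(a)], with σX = √(10² + σe²) and a = (20 − μ) / σX.

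- μ = 20, σe = 5: σX = √125 = 11.18, a = 0, ratio = 0.798. Gain = 25 / 11.18 × 0.798 = 1.78 points.
- μ = 35, σe = 3: σX = √109 = 10.44, a = −1.437, ratio = 0.154. Gain = 9 / 10.44 × 0.154 = 0.13 points.

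| Candidate mean | σe = 3 | σe = 5 | σe = 8 |
|---|---|---|---|
| 20% | 0.69 | 1.78 | 3.99 |
| 25% | 0.45 | 1.20 | 2.83 |
| 30% | 0.26 | 0.73 | 1.88 |
| 35% | 0.13 | 0.40 | 1.14 |

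**4. Consequence for the stated test (simulation, one arm, n = 12).** An upward significant paired Wilcoxon result occurs in about 5–21% of trials for candidate means of 20–25%, and in about 3–8% for means of 30–35%. Exact or approximate p-values move the top figure by about 2 points. Between 51% and 65% of patients show an increase; noise alone gives about 50%.

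**5. A model closer to the plan's two scales.** Here entry uses the ratio to two neighbouring discs, each read with error, and the outcome is millimetres of the affected space. Further assumptions are healthy height 10 mm, candidate means of 15–35% and reading error of 0.3–1.0 mm. The spurious gain is 0.01–0.67 mm, and upward significance at n = 12 occurs in 3–37% of trials. The wider range reflects the wider inputs.

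**6. Does a new V0 film cure it?** If the new film plays no part in eligibility, yes: mean gain 0.00 and upward significance in about 2–3%. If the 20% rule is applied again to that film, about 57–72% of the bias remains for candidate means of 20–25%.

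**7. Between arms.** Randomisation gives both arms the same expected regression. In every scenario the simulated between-arm difference in change was about zero, with two-sided rejection of about 4–5.5%.

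**The case against.** The other side has four good arguments.

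- **The premise is conditional.** A reader of the schedule table might infer that the qualifying reading is always the baseline. The documents do not support that. Sections 4.2 and 7.2.1 order new reference films unless a recent valid one exists, and 7.2.1 places the reference measurements after the eligibility check. What stands is that the table and the waiver permit one film to do both jobs, and that the re-check at V0 can turn a new film into a second gate.
- **There is a control arm.** A reader might also infer that the efficacy comparison is biased. It is not (step 7). Section 3.2 makes comparison with control an objective, 11.2 gives a between-group test, 11.3.7 compares signs of regeneration between interventions, and 11.5 says the placebo effect must be discounted. However, 11.2.1.1 applies none of this to height, and its interpretation sentence needs no comparison with control.
- **Height is not clearly central.** Section 7.1.1 omits it from the main evaluation variables, 11.2.1 ties regenerative efficacy to MRI, and the main objective is feasibility and safety. That limits the stakes, although 3.3.1 still calls height primary.
- **The size depends on chosen inputs.** With candidates well past 20% and small error, the effect is close to nil. Entry uses a ratio and the outcome uses millimetres, and the plan standardises technique and time of day, which limits error. All of this stands. Larger rejection rates could be obtained by pooling the 24 patients, but the plan states no such analysis.

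**Conclusion.** The point holds in a conditional form. Where the qualifying film is also the baseline, or a new V0 film is held to the 20% rule again, within-arm height change is biased upward, and 11.2.1.1 as written would allow that rise to be called rehydration.

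The size cannot be derived from the documents. Under the assumptions in step 2 it is about 0.1–4 points of neighbour height (0.01–0.4 mm on an assumed 10 mm space), with a one-arm upward significant result in about 3–21% of trials against 2.5% nominal. It is material when many candidates lie near the cut-off and reading error is sizeable, and negligible otherwise. Separately, about half of unchanged patients would show an increase from noise alone, so a rule without a minimum change says little about any one patient.

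This is a weakness of one stated analysis and its interpretation. It should be corrected, but it does not undermine the randomised comparison.

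**What to change.** 1. In 11.2.1.1, make the between-arm difference in height change at 6 and 12 months, adjusted for baseline height, the stated height analysis. Keep the paired within-arm test as descriptive only. Section 11.2 names no adjusted method, so one must be added.
2. Replace the interpretation sentence there, and its counterpart in 3.3.1, with a statement such as: a within-arm rise in height is not by itself evidence of rehydration, because entry selects low readings.
3. Take baseline from a reading not used for inclusion criterion 3. The same reader re-reads the existing baseline film, blind to arm and time point, in one batch with the 6- and 12-month films. Where a separate V0 film exists and was not used to apply the 20% rule, use that film as baseline.
4. Reconcile 4.2, the schedule table in 7.2 and the Visit 0 text in 7.2.1 on which film is the baseline.

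**Cost.** Wording changes and one re-reading of the existing films, with no new films or patients. Re-reading removes reading error but not positioning error: if positioning made up half of the error variance, about half of the within-arm bias would remain, which is why item 1 matters most. The within-arm interpretation becomes less favourable, and the between-arm test is weak at this size: with 12 per arm, 80% power needs a standardised difference of about 1.14.

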3.2. Secondary objectives

□ To determine clinical outcomes and image variations

Radiographic and Magnetic Resonance, which denote anti-inflammation, regeneration or, on the contrary, progression of lumbar IVD deterioration, after 12 months after the implementation of MSV in the NP.

□ Compare the efficacy of MSV treatment with that obtained in the arm control.

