11.2.1.2 Quantitative MRI criteria

Quantitative density evaluations will be carried out in the "ROIs" (Regions of interest) of the area of the nucleus pulposus of the affected segment and of the 3-5 healthy neighboring segments in the T2 images taken before the start of treatment and 6 and 12 months after inclusion. The quotient of the value obtained in the affected segment divided by the mean of the healthy segments will be used as a measure of the relative water content, with 1.00 being the normal value. The same ROIs should be used for the measurements obtained at 3 times, before treatment and 6 and 12 months after. The procedure is illustrated in Figure 4 (taken from (Orozco et al., 2011)). The increase

in the quotient approaching the value of 1 is will consider a sign of rehydration. The descriptive analysis of the values of this variable It will be expressed by the mean, standard deviation, 95% confidence interval of the mean.

To find out if there are differences between baseline and at 6 and 12 months, the no test will be used. parametric for paired Wilcoxon data.

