11.3.4 Analysis methods

Descriptive statistics will be made including summary statistics and lists. For the comparisons of means at 0, 6 and 12 months a comparison of means using the t-test or Wilcoxon test as appropriate (see 11.2).

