11.3.7 Efficacy

Changes in pain, disability and quality of life indices will be described in the baseline situation and at 3, 6 and 12 months of treatment, which will be compared as specified in 11.2.

The frequency and percentage of patients presenting signs of regeneration at 12 months of the different interventions, comparing the values as specified in 11.2.

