11.5. DIFFICULTIES AND LIMITATIONS OF THE STUDY

As noted above, previous clinical trials show that a considerable improvement (up to 30%) due to the placebo effect. It will therefore be accurate discount this random effect before assessing the effects of MSVs. It is therefore, important evolution in the control group.

Bone marrow donation could be a problem if not enough were found donors. The solution to be used, when possible, by patients undergoing treatment with autologous mesenchymals (in the trial we are conducting in collaboration with CM Teknon) also as allogeneic donors would be the situation ideal, the most economical in terms of required means and the most interesting scientifically.

We have tried to obtain the maximum masking in the test within a design reasonable for this first study. While the "single blind" (patient) design is feasible without serious complications, the "double blind" (researcher) or "triple" (analysis) various logistical and ethical issues, so they have been left for the future. If there are indications of efficacy for allogeneic MSV, it will not be possible to perform direct comparison with autologous MSVs, so if these are obtained results, a new trial should be designed to directly compare the efficacy of both therapeutic alternatives.

REFERENCES:

Adams MA, Dolan P & Hutton WC. (1986). The stages of disc degeneration as revealed by discograms. The Journal of bone and joint surgery 68, 36-41. Adams MA, Freeman BJ, Morrison HP, Nelson IW & Dolan P. (2000). Mechanical initiation of intervertebral disc degeneration. Spine (Phila Pa 1976) 25, 1625-1636. Aggarwal S & Pittenger MF. (2005). Human mesenchymal stem cells modulate allogeneic immune cell responses. Blood 105, 1815-1822.

Bernardo ME, Locatelli F & Fibbe WE. (2009). Mesenchymal stromal cells. Ann N Y Acad Sci 1176, 101-117.

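### Disc height and the T2 quotient are given only a paired before-after test; the between-arm comparison has to be inferred and is not baseline-adjusted.

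*Combined protocol and SAP*

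**What the plan says.** - **Disc height, 11.2.1.1:** descriptive statistics and one test, for "differences between baseline and at 6 and 12 months the Wilcoxon nonparametric test for paired data will be used". An increase in height is to be read as a sign of rehydration.
- **T2 quotient, 11.2.1.2:** the same, in garbled translation: "differences between baseline and at 6 and 12 months, the no test will be used. parametric for paired Wilcoxon data". Neither subsection mentions the control arm or says whether the test is run per arm or on all patients pooled.
- **General rule, 11.2:** to assess "differences between the two groups, a normality analysis of the distribution will be carried out", followed by a t-test or a Wilcoxon test. No covariate is mentioned.
- **11.3.4:** "comparisons of means at 0, 6 and 12 months a comparison of means using the t-test or Wilcoxon test as appropriate (see 11.2").
- **11.3.7:** the frequency and percentage of patients with "signs of regeneration at 12 months of the different interventions, comparing the values as specified in 11.2".
- **Aims:** 3.2 lists as an objective "Compare the efficacy of MSV treatment with that obtained in the arm control". Section 11.5 expects up to 30% improvement from placebo and says one must "discount this random effect before assessing the effects of MSVs". Section 3.3 lists disc height and MRI water content as primary criteria.

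**The concern.** A randomised control arm is there so that change common to both arms can be subtracted. The only test named in the two imaging subsections does not use that arm. If its p-value were reported as evidence of efficacy, natural course, concurrent physiotherapy, measurement drift and regression to the mean would all count in favour of MSV.

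For disc height the design itself offers one such shared source. Patients enter on "Decrease in the height of the disc space of more than 20% measured" on the lateral film. The schedule in 7.2 puts the lumbar X-ray at pre-inclusion, and 7.2.1 allows films up to 6 months old in place of new ones. The film that qualified the patient can therefore also be the baseline film. Discs whose measured height was low partly by error would then tend to measure higher at 6 and 12 months in both arms, and 11.2.1.1 would read this as rehydration.

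Leaving open whether follow-up values or changes are compared also allows the choice to be made after the data are seen. With 12 per arm, chance baseline imbalance is plausible and the two choices can disagree.

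**Working it through.** **1. What the text specifies.** The plan gives no figure to reproduce: 11.1 fixes 12 per arm without effect size, SD or power. The routes by which a between-arm test could reach the imaging variables are these.

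| Route | What it gives | What stays open |
|---|---|---|
| 11.2 as parent section | t-test or Wilcoxon between groups | The subsections name a different test; value or change not stated |
| 11.3.4, pointing to 11.2 | Comparison of means at 0, 6 and 12 months | Whether time points or arms are compared |
| 11.3.7, pointing to 11.2 | Regeneration signs across interventions | A frequency, for which a test of means does not fit; not height in mm or the quotient |

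The only place that ties change from baseline to 11.2 is 11.3.6, for laboratory parameters. No baseline-adjusted model appears anywhere in section 11.

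**2. Paired test when both arms change equally.** Inputs from the plan: 12 per arm (11.1) and two-sided 5% (11.2). Assumed: normal changes and an equal mean change *d* in both arms, in units of the SD of change. The exact signed-rank test at n = 12 rejects when the smaller rank sum is 13 or less (attained level 4.2%).

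| *d* in both arms | MSV-arm paired test significant | MSV significant, control not | Between-arm t-test on change |
|---|---|---|---|
| 0 | 4% | 4% | 5% |
| 0.3 | 14% | 12% | 5% |
| 0.5 | 31% | 22% | 5% |
| 0.8 | 67% | 22% | 5% |
| 1.0 | 85% | 13% | 5% |

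**3. Regression to the mean in disc height.** Assumed: no true change; selection of the most extreme fraction *q* on the observed baseline; reliability ρ; observed SD 1. With z the cut-off and i = φ(z)/q, the mean shift is (1−ρ)i. The variance of change is (1−ρ)²[1−i(i−z)] + (1−ρ²).

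For q = 0.2, ρ = 0.7: i = 1.40 and z = 0.84, so the shift is 0.3 × 1.40 = 0.42. The variance is 0.09 × 0.22 + 0.51 = 0.53, so the SD is 0.73. The standardised shift is 0.42/0.73 = 0.58.

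| q | ρ | Shift, SD of change | Paired test significant |
|---|---|---|---|
| 0.2 | 0.70 | 0.58 | 40% |
| 0.2 | 0.90 | 0.32 | 15% |
| 0.5 | 0.80 | 0.26 | 11% |
| 0.5 | 0.95 | 0.13 | 6% |
| 0.8 | 0.95 | 0.06 | 5% |

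**4. What baseline adjustment gains.** With equal SDs and baseline-to-follow-up correlation r (not in the plan, so a range), the large-sample variance ratio of ANCOVA is 1−r² against follow-up values. Against change scores it is (1−r²)/(2(1−r)) = (1+r)/2. Estimating the slope with 22 within-arm degrees of freedom multiplies both by 1 + 1/20 = 1.05.

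| r | Against follow-up values | Against change scores |
|---|---|---|
| 0.3 | 0.91 × 1.05 = 0.96 | 0.65 × 1.05 = 0.68 |
| 0.5 | 0.75 × 1.05 = 0.79 | 0.75 × 1.05 = 0.79 |
| 0.7 | 0.51 × 1.05 = 0.54 | 0.85 × 1.05 = 0.89 |
| 0.9 | 0.19 × 1.05 = 0.20 | 0.95 × 1.05 = 1.00 |

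Simulation agrees to within 0.01. Simulated power for a 1.0 SD difference at r = 0.3, 0.5, 0.7 is 67%, 75%, 89% by ANCOVA and 51%, 65%, 86% by change scores; on follow-up values it is 65% throughout. The simulated type I error of ANCOVA is 4.9% to 5.1%.

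**The case against.** The strongest reply is that the between-arm test is already there. Sections 11.2.1.1 and 11.2.1.2 sit under 11.2, a parent section normally governs its children, and 0, 6 and 12 months in 11.3.4 is exactly the imaging schedule. Section 11.5 shows that the authors mean to use the control arm, and some of the ambiguity may come from translation. This stands to the extent that it would be wrong to say no between-arm test is planned. It does not settle whether 11.3.4 compares arms or times, or whether values or changes are used.

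Second, the rejection rates in step 2 describe a misuse that the plan does not announce. That is fair: they apply only if the paired test is read as evidence of efficacy. But it is the only test named in the two subsections, and 11.2.1.1 attaches a biological reading to a rise.

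Third, 5.2.2.1 defines the 20% loss relative to healthy adjacent segments, while step 3 selects on the height itself, and both its inputs are assumed. Selecting on that ratio instead gave a similar or larger shift (0.06 to 0.72 SD), so the mechanism survives, but its size remains hypothetical. True patient-to-patient variation in change would reduce the standardised shift, and at the low end there is practically no effect.

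Fourth, an unadjusted two-group comparison is valid under randomisation, so ANCOVA is a gain in precision and not a condition of validity. This is correct, and near r = 0.9 it gains nothing over change scores. Two smaller points also stand: a nonparametric fallback should be kept at 12 per arm, and with one or two affected discs per patient (5.1.1) the unit analysed should be stated.

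**Conclusion.** The concern holds, as a point to clarify. The two imaging subsections name only a paired test, the two-group rule reaches them indirectly, and no baseline-adjusted between-arm analysis is specified, although comparison with control is an objective. That textual finding is secure.

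The size rests on assumptions. An equal change of 0.3 to 1.0 SD in both arms makes the MSV-arm paired test significant in 14% to 85% of trials. Regression to the mean alone does so in about 5% to 40%, if the cut selects 20% to 80% of screened discs and reliability is 0.70 to 0.95. ANCOVA cuts variance by about 5% to 80% against follow-up values and by 0% to about 30% against change scores, for r from 0.9 down to 0.3 in the latter case. Efficacy is secondary and preliminary here, and the feasibility and safety objective is not affected.

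**What to change.** In 11.2.1.1 and 11.2.1.2, and by cross-reference in 11.3.4, state that:

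- efficacy inference is the MSV-minus-control difference at 12 months (main) and at 6 months;
- it is estimated by ANCOVA of the follow-up value on arm with the baseline value as covariate, and reported with its 95% CI;
- paired changes are reported per arm, descriptively.

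In the same text, name the unit of analysis for patients with two treated discs, and keep the Wilcoxon comparison of changes between arms as the fallback if residuals are clearly non-normal. The same model can serve VAS, ODI and SF-12 under 11.3.7.

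The cost is a written amendment under 9.2, with AEMPS and CEIC approval when required. No patients, visits or measurements are added, since baseline values are already collected. Another package may be needed if the software in 11.4 cannot fit ANCOVA. The sponsor gives up the option of reporting a within-arm change as efficacy.
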